8.2.2.5 Pregnancy Reporting

Although pregnancy is not considered an AE, the Investigator (or his or her designee) is

responsible for recording in the subject's source document any pregnancy during or within 6

months after completing infusion. All subjects who become pregnant must be followed by the

Investigator until the end of the pregnancy to determine the outcome. The outcome of the birth

(health of infant) must be reported to the Medical Monitor.

9 Statistical Methods

The primary efficacy analysis of OS will be assessed according to a single-arm, single-stage

design on the ITT population. OS will be determined via Kaplan-Meier estimation, with medians,

quartiles, and 95% confidence intervals (CIs) reported. mOS will tested using a single sample one

sided log-rank test on a 10% significance level against historical control.

A secondary analysis of the primary variable will be conducted in the IL4-R population according

to IL4-R status.

PFS will be assessed and summarized as OS.

Descriptive analysis of the OS and PFS at 6, 9, and 12 months after treatment will be based on the raw proportions of subjects surviving (and progression-free) at those time points as well as Kaplan-Meier estimation. Further analyses will also be conducted by IL4R stratum, including examination of the treatment effect by IL4R level.

Efficacy analyses may also explore subject subsets (e.g. IL4R level, tumor size, KPS, gender, age, steroid use,) and response by other applicable criteria.

Descriptive statistics will be provided for subject demographics and disposition, safety, and exposure data and will include the number of observations, mean, standard deviation, median, and range for continuous variables and number and percent for categorical variables; 95% Cls will be presented where appropriate.

9.1 Determination of Sample Size

The sample size is calculated for the primary analysis and based on the following assumptions: uniform accrual over time, no loss to follow-up, exponentially distributed death times, use of the exponential MLE test, follow-up time 12 months and a one-sided test on a 10% significance level. With a null hypothesis of a median OS of 8 months and an alternative hypothesis of 11.5 months the power for the primary test will be over 80% with 46 evaluable subjects.

9.2 Statistical and Analytical Plans

The primary analysis will occur when median survival is reached (> 50% of all subjects have died) or all subjects have completed the Day 360 visit or discontinued prior to completing the Day 360 visit whichever happens last. Collection of follow-up data will continue until all patients have withdrawn from follow-up. Supplementary reports, presenting updated time-to-event data, will be prepared after completion of the 2-year survival follow-up period and beyond, if required.

Descriptive statistics will be presented including the number and percent for categorical variables and the number of observations, mean, standard deviation, median, and range for continuous variables; 95% confidence intervals (CIs) will be presented as appropriate.

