Post-treatment follow-up assessment of safety will be performed 14 days after CED infusion. Thereafter, efficacy and safety assessments will be performed at 30, 60, 90 and 120 days after CED infusion and every 8 weeks thereafter until 360 days of active follow up have been completed. Subjects who discontinue before the Day 360 visit will undergo all the procedures scheduled for the Day 360 visit at the time of discontinuation. Subjects who complete the Day 360 assessment without disease progression or discontinue early without disease progression will continue to be followed for disease status until progression where possible. After progression (on study or during post-study follow-up), subjects will continue to be followed, where possible, for survival, post-study treatment(s) for GB and imaging for GB until death (or termination of data collection by the Sponsor or withdrawal of consent by the subject). MDNA55 drug product is supplied as a sterile frozen solution at a concentration INVESTIGATIONAL of PRODUCT AND **ROUTE OF** labeled according to country-specific regulatory ADMINISTRATION: requirements. For clinical use, MDNA55 drug product will be diluted in Elliotts B® solution to produce an infusate of MDNA55 consisting of human serum albumin and gadolinium-diethylenetriamine pentaacetic (Gd-DTPA, acid Magnevist®). The infusate is prepared at the hospital pharmacy and instructions for its preparation are provided in the Pharmacy Manual. MDNA55 is administered via infusion using CED with precision planning and real-time MRI monitoring of infusate distribution. DOSAGE AND FREQUENCY: The total dose will not exceed 240 µg (the established MTD). At the discretion of the Investigator a subject may be eligible to receive a second administration of MDNA55. **EFFICACY Primary ENDPOINTS:** mOS, defined as the time from treatment until death Secondary mOS by tumor IL4-R status OS12 (proportion of subjects surviving 12 months) ORR as determined by an independent central review according to RANObased criteria incorporating advanced imaging modalities (e.g. diffusion, perfusion and/or TRAMs) PFS, defined as the time from treatment until disease progression or death.

| | Other Duration of response (DOR), defined as the time from first response until disease progression or death among those subjects achieving a complete response (CR) or partial response (PR) to treatment. |
|---|---|

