7.1 Efficacy Evaluation

7.1.1 Survival

After progression (on study or during follow-up), subjects will continue to be followed for survival and post-study treatment(s) for GB and imaging for GB, where possible, until death (or termination of data collection by the Sponsor or withdrawal of consent by the subject).

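### The primary-analysis trigger counts leaving the study as the end of follow-up, so late entrants can fall short of the 12 months of survival follow-up that the sample size assumes

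*Protocol*

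**What the plan says.** Protocol section 9.2 places the primary analysis at the later of two conditions. One is "when median survival is reached (> 50% of all subjects have died". The other is that "all subjects have completed the Day 360 visit or discontinued prior to completing the Day 360 visit whichever happens last".

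Section 4.4 lists confirmed progression, an adverse event and the start of further glioblastoma treatment among the reasons for withdrawal. None of these ends survival follow-up. Section 7.1.1 states that after progression "subjects will continue to be followed for survival", and sections 7.5.4 and 7.5.5 move subjects withdrawn before Day 360 into post-study follow-up.

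Section 9.1 bases the sample size on "uniform accrual over time, no loss to follow-up, exponentially distributed death times, use of the exponential MLE test" and on "follow-up time 12 months and a one-sided test on a 10% significance level". For medians of 8 months (null) and 11.5 months (alternative), it states that "the power for the primary test will be over 80% with 46 evaluable subjects". No accrual period is given.

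The Synopsis lists "OS12 (proportion of subjects surviving 12 months" as a secondary endpoint. The opening of section 9 reports 12-month survival both as a raw proportion and by Kaplan-Meier. SAP section 7.7.1 estimates 6-, 9- and 12-month survival by Kaplan-Meier and censors at last contact. The SAP sets neither an analysis date nor a minimum survival follow-up.

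**The concern.** The second condition measures participation in the active study, whereas the endpoint is death. A subject withdrawn alive at month 3 meets the condition at month 3, although survival follow-up has only begun. Once more than half the subjects have died, the analysis may run as soon as the last subject leaves active follow-up. Some late entrants may then be alive with less than the 12 months that section 9.1 assumes.

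Three things are at stake: deaths available to a test that has little power to spare, a known 12-month status for the raw survival proportion, and an analysis date that does not move with withdrawal decisions.

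**Working it through.** **1. The plan's own power.** Inputs from section 9.1: N = 46, one-sided 10%, medians 8 and 11.5 months, exponential survival, F = 12 months after accrual ends. Accrual A is an assumption.

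- Hazard under the alternative: L = ln 2 / 11.5 = 0.0603 per month.
- Log ratio: ln(11.5/8) = 0.363.
- Deaths needed for 80% power: ((1.282 + 0.842)/0.363)² = 34.2.
- Expected deaths: d = N·[1 − (exp(−L·F) − exp(−L·(A+F)))/(L·A)].
- Power = Φ(√d · 0.363 − 1.282).

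For A = 24: d = 46·[1 − (0.485 − 0.114)/1.447] = 34.2 and power is 80.0%. For A = 12, 18, 30 and 36 months, power is 76.1%, 78.3%, 81.2% and 82.2%. Other forms of the test reach 80% from about 12 months of accrual (one-sample log-rank 80.6%, test on the mean scale 80.3%) or 18 months (cube-root scale 80.4%). The claim of over 80% is therefore attainable with 12 months of follow-up and accrual of at least about 12 to 24 months. It cannot be reproduced exactly without the accrual period.

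**2. The trigger as written.** 20,000 trials were simulated per case, with uniform accrual over 24 months (assumed) and exponential survival with median 11.5 months. Subjects leave at progression or death, with an assumed median of 2.5, 4 or 5.75 months. The 4-month value borrows the null median for progression-free survival in section 9.2.5.2. The analysis date is the later of the death that takes the total past 50% and the last Day 360 visit or departure. The comparison is an analysis 12 months after the last entry.

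| Median time to progression or death (months) | 2.5 | 4 | 5.75 |
|---|---|---|---|
| Last entrant's potential follow-up, median (months) | 7.7 | 10.1 | 11.0 |
| Living subjects censored before Day 360 | 5.1 | 2.5 | 1.5 |
| The same as a share of 46 | 11% | 5% | 3% |
| Deaths lost | 3.7 | 1.9 | 1.1 |
| Power lost (points) | about 3 | 1 to 2 | just under 1 |

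The count of censored subjects is the least stable row. In the 4-month case it runs from 2.3 to 3.0, depending on modelling details such as whether Day 360 or a full 12 months is the yardstick.

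Hand check of the 4-month case: deaths fall from 33.8 to 32.0. The formula gives Φ(√33.8 · 0.363 − 1.282) = 79.6% and Φ(√32.0 · 0.363 − 1.282) = 78.0%, a loss of 1.6 points. The simulated figures are about 81% and 79%.

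**3. How often.** In the 4-month case the last entrant has less than Day 360 of potential follow-up in 87% of trials, less than 9 months in 31% and less than 6 months in 5%. The condition on deaths sets the date in only 0.7% of these trials, so it rarely protects late entrants. With 12 months of accrual and a 3-month median it does so in up to 14%.

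**4. Other accrual lengths.** Over 12 to 30 months of accrual and medians of 3 to 6 months, power is 74–81% as written and 77–81% with 12 months for everyone, a cost of about 0 to 3 points. Simulation error is about 0.3 points.

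**5. Validity.** Under the null, simulated type I error is near 9% with either rule (checked at a 4-month median). In the 4-month case the mean Kaplan-Meier 12-month survival is 0.485 as written and 0.484 with full follow-up, against a true value of exp(−0.0603·12) = 0.485. The standard deviations are 0.076 and 0.075.

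**The case against.** The strongest reply is that the effect is small. The condition needs every subject, so a single late entrant who stays to Day 360 pushes the date out. The 87% includes shortfalls of days, and trials in which the last entrant has already died and nothing is lost. A 2.5-month median lies below the plan's own null of 4 months for progression-free survival. It also fits poorly with the advice in section 1.4.1 to keep subjects on study for at least 120 days. All of this stands, and the 2.5-month column is best read as the adverse end. Delaying progression withdrawals to Day 120 did not materially change the results. On the other side, if death is added as a cause of leaving on top of the assumed discontinuation rate, the power loss rises to 2.6 points at 4 months and 1.4 at 5.75.

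Kaplan-Meier handles the censoring, and SAP section 4.2 does not list 12-month survival as a separate secondary endpoint. This also stands, and it confines that harm to the raw proportion in protocol section 9.

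Section 9.2 says when the analysis occurs, while section 8.1.1 refers to a data-inclusion cut-off whose date is not fixed. Treating the two as the same date is an inference. Data collection continues and updated reports are planned after 2-year survival follow-up, which limits lasting harm but leaves the primary test unchanged.

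A reader might infer that the rule is a leftover from the time when response was the primary endpoint. No passage gives its origin, and the condition on deaths is itself a survival criterion.

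**Conclusion.** The point holds as a modest design weakness that is cheap to remove. The trigger does not guarantee the 12 months of survival follow-up assumed in section 9.1, and nothing in the SAP supplies it. The cost is about 1 to 4 deaths, up to about 3 points of power at 24 months of accrual, and an undetermined raw 12-month status in roughly 1.5 to 5 of 46 subjects. These figures rest on assumed accrual, assumed discontinuation times and exponential survival.

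Two stronger readings are not supported. One is that late entrants are typically cut off far short of 12 months: in the 4-month case the median shortfall for the last entrant is 12 − 10.1 = 1.9 months, and follow-up under 6 months is uncommon. The other is that investigators' withdrawal decisions in an open-label trial bias the result: the date does depend on them, but no bias or type I error inflation is shown.

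**What to change.** Keep the condition that more than 50% of subjects have died. Replace the second condition with: every treated subject has died, has withdrawn consent for or been lost to survival follow-up, or has at least 12 months (365 days) of survival follow-up from the start of infusion with vital status confirmed, whether or not still on study. Naming 365 days matters because Day 360 is 11.8 months, and Day 353, the early edge of the visit window, is 11.6.

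State the same rule in the SAP, with the data cut-off date tied to it, and give the accrual period behind the power figure.

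The cost is one sentence in each document and a later primary analysis. From the table, the median delay is about 12 − 11.0 = 1.0, 12 − 10.1 = 1.9 or 12 − 7.7 = 4.3 months, so roughly 1 to 5 months. Survival data are already collected after withdrawal, so no new data collection is needed beyond confirming vital status at the cut-off.

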9.2.1 Randomization

This study is a single-arm design. All subjects will receive active treatment. No randomization will be performed.

9.2.2 Analysis Populations

Following quality review of study images mid-way through recruitment, local tissue reactions, inflammation, immune cell infiltration, edema and/or necrosis, subsequent to MDNA55 administration, was observed in some subjects and has been seen to be indistinguishable from possible tumor growth using the imaging techniques adopted from the outset of this study. Therefore, obtaining reliable imaging data for the primary efficacy analysis has been shown to be confounded. Consequently, under protocol version 6.0, the surrogate endpoint Objective Response Rate (ORR) will be assessed as a secondary outcome measure with the median Overall Survival (mOS) becoming the primary variable.

9.2.2.1 Intent to Treat (ITT)

An ITT population will comprise all subjects who receive any amount of study drug will be used for the primary efficacy analyses, other purely survival-based endpoints and all safety analyses.

A modified ITT population for secondary imaging-based analyses, including PFS, (mITT, see below) will comprise all subjects who receive any amount of study drug and have adequate imaging or clinical data for the ORR analysis. NOTE: Patients who expire or progress clinically prior to the first MRI examination will not be evaluable for any of the response assessments.

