9.2.2.2 Per Protocol (PP) Population

The PP population will comprise all patients in the ITT population (or mITT for imaging-based endpoints) who also have no major protocol violations during the study. This population will be finalized prior to the final lock and primary analysis of the study data. Efficacy analyses will be conducted on this population in support of the primary efficacy results.

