5.2 Modified Intent to Treat Population (mITT)

A modified ITT population for secondary response analyses (mITT) will comprise all subjects who receive any amount of study drug and have adequate imaging (at least 1 post-treatment scan) and clinical data for the ORR analysis.

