5.3 Per Protocol Population (PP)

The PP population will comprise all subjects in the mITT population who also have no major protocol violations during the study. Efficacy analyses will be conducted on this population in support of the primary efficacy results.

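### Protocol 9.2.2.1 analyses PFS in a set that can leave out subjects who fail before their first MRI, which biases PFS toward success; the documents conflict on the PFS set and need reconciling

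*Protocol*

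**What the plan says.** **PFS set.** Protocol 9.2.2.1 describes "A modified ITT population for secondary imaging-based analyses, including PFS", whose members received any study drug and "have adequate imaging or clinical data for the ORR analysis". Its note adds: "Patients who expire or progress clinically prior to the first MRI examination will not be evaluable for any of the response assessments". SAP 5.2 is stricter and asks for "adequate imaging (at least 1 post-treatment scan) and clinical data for the ORR analysis". The ITT set, by contrast, "will be used for the primary efficacy analyses, other purely survival-based endpoints and all safety analyses".

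**PFS event and test.** Protocol 9.2.5.2 counts PFS from the start of infusion. Its events are radiologic progression, neurologic progression and death from any cause, and it tests PFS against a 4-month median at the 10% level. Protocol 9.4 makes that test one-sided and places it directly after OS in the hierarchy. Protocol 8.1.2 instead requires confirmed objective progression or death, and SAP 7.7.2 requires confirmed progression or death.

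**Sections that point elsewhere.** The protocol synopsis and SAP 5.2 describe mITT as a set for response analyses. Protocol section 9 says PFS is handled in the same way as OS. SAP 7.7.2 names no set for PFS and gives Kaplan-Meier estimates and intervals without the 4-month test. SAP section 9, on changes from the protocol, lists nothing.

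**Per-protocol set.** SAP 5.3 reads: "The PP population will comprise all subjects in the mITT population who also have no major protocol violations during the study". The protocol synopsis says the same. Protocol 9.2.2.2 draws the set from ITT, and from mITT only for imaging-based endpoints.

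**The concern.** If membership of the PFS set requires reaching a post-treatment scan without dying or progressing clinically, it depends on not having had an early PFS event. Subjects who stay in are credited with event-free time from Day 0, while those who failed in that time are dropped. A single-arm trial has no comparator in which the same selection could cancel.

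What is at stake is the second test in the hierarchy and the reported PFS median and intervals. The distortion is greatest if surgery or infusion causes early harm, because that harm is then removed from the PFS result. Drawing the per-protocol set from mITT carries the same selection into the analysis meant to support the OS result.

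**Working it through.** **Plan's own figure.** Neither document gives a power or sample size for PFS. The only figure to compare with is the nominal 10% one-sided level. The power statement in Protocol 9.1 is for OS and does not bear on this point.

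**Inputs from the documents.** About 52 treated subjects (Protocol 4.1); null median 4 months (9.2.5.2); 10% one-sided (9.4); first follow-up MRI at Day 30, and an earlier scan 18–30 hours after the end of infusion (Tables 6 and 7).

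**Assumptions.** Exponential PFS, 30.44 days per month, 12 months of follow-up, and accrual of 0 or 24 months, since no accrual period is stated. The number of early failures left out is also assumed and is shown as a range.

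**Step 1: events before the first MRI under the null.**
- By Day 30: 1 − 2^(−(30/30.44)/4) = 0.157, and 0.157 × 52 = 8.2 subjects.
- By Day 3, roughly when the 18–30 hour scan falls: 1 − 2^(−(3/30.44)/4) = 0.0169, and 0.0169 × 52 = 0.9 subjects.

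**Step 2: direction.** The test statistic is (O − E)/√E, with rejection below −1.2816. The monthly hazard is ln 2/4 = 0.1733. A subject who fails by Day 30 adds 1 to O and at most 0.1733 × 30/30.44 = 0.17 to E. Removing that subject lowers O − E by at least 0.83, which is always toward success.

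**Step 3: simulated rejection rate at a true median of 4 months, n = 52.**

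| Subjects left out | No accrual spread | 24-month accrual |
|---|---|---|
| None | 8.7% | 8.8% |
| All events before Day 3 (about 0.9) | 11.1% | not run |
| 25% of events before Day 30 (about 2) | 13.7% | 13.1% |
| 50% of events before Day 30 (about 4) | 20.6% | 19.5% |
| All events before Day 30 (about 8) | 40.9% | 38.4% |

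Removing exactly 1, 2 or 4 early failures, with no accrual spread, gives 11.5%, 14.2% and 21.0%. These rates are for the PFS test by itself; it is reached only if OS succeeds.

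**Hand check.** With 12 months of follow-up, E averages 52 × (1 − 2^(−12/4)) = 45.5, so √E = 6.75. An early failure averages about 15 days, so its share of E is 0.1733 × 15/30.44 = 0.085. Each removal moves the statistic by about 0.915/6.75 = 0.136. The 8.8% baseline corresponds to a normal quantile of −1.353. Two removals give Φ(−1.353 + 0.271) = 14%, and four give Φ(−1.353 + 0.543) = 21%.

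**Step 4: apparent median.** If a fraction q is removed early, the Kaplan-Meier median becomes −ln((1 − q)/2)/0.1733. For q = 2/52 this is 4.2 months, and for q = 4/52 it is 4.5 months, against a true 4.0. This shift does not depend on whether the 4-month test is run.

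**Step 5: per-protocol OS.** Under the 8-month OS null, 1 − 2^(−(30/30.44)/8) = 0.082, or 4.3 of 52 subjects, die by Day 30. By Day 3 the figure is 1 − 2^(−(3/30.44)/8) = 0.0085, or 0.4 of 52. These are the most that the scan requirement would remove from the supportive OS analysis on each reading, under a constant hazard.

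**The case against.** The strongest reply is that exclusion is one reading among several. The note in 9.2.2.1 speaks of response assessments, not PFS. The protocol's wording accepts imaging or clinical data, which could keep a subject with documented clinical progression. Section 9 aligns PFS with OS, and SAP 7.7.4 assigns mITT by name to DOR, DOCB and TTP while SAP 7.7.2 does not do so for PFS. This stands against any claim that early failures will certainly be deleted. It does not remove the problem: 9.2.2.1 still names PFS under mITT, SAP 5.2 still demands a scan, and no all-treated PFS analysis is specified by name.

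Second, the first MRI is undefined. Read literally, the 18–30 hour scan satisfies SAP 5.2, and the effect is then small (about 11%). This also stands, and it is why a range is given.

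Third, a reader might infer from Step 1 that about 8 subjects would be lost and the error would reach 38–41%. The documents do not support that. Purely radiologic progression is not seen before a scan, so the rule cannot remove it. Protocol 8.1.3 wants neurologic decline confirmed by advanced imaging or biopsy, and 1.4.1 does not register edema-related worsening automatically as progression. Entry requires a life expectancy of at least 12 weeks and KPS of at least 70 (4.2.1), so a constant hazard from Day 0 may overstate early events.

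Fourth, the 4-month test is in the protocol only. The SAP omits it without listing the omission as a change, so the false-positive argument applies to the protocol's test. The upward shift of the median applies to both documents if mITT is used.

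**Conclusion.** The point holds in this form. Protocol 9.2.2.1, read with its note and SAP 5.2, allows subjects who have already met a PFS event definition to be left out because the event came early, and other sections disagree on the set. The direction of the bias under that rule is certain; its size is not. On the assumptions above, the nominal 10% test rejects about 9% with all treated subjects kept, about 11% if the 18–30 hour scan is the first MRI, about 14% with two early failures removed and about 20% with four. The 38–41% row is an upper bound that cannot be reached in practice.

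A reader might also infer that the SAP alone introduced the per-protocol defect, or that the primary result is compromised. Neither is supported. The protocol synopsis already draws the per-protocol set from mITT, so the conflict lies within the protocol. Primary OS is analysed in ITT and is unaffected. Since PFS is secondary and tested only after OS succeeds, this is a should-fix.

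**What to change.** 1. State in Protocol 9.2.2.1 and SAP 7.7.2 that PFS is analysed in all treated subjects (ITT), with death before the first MRI an event on the date of death.
2. Reconcile Protocol 1.4.1, 8.1.2, 8.1.3 and 9.2.5.2 into one PFS event definition, and handle early clinical progression under it.
3. Keep mITT for response and as a PFS sensitivity analysis. Align the protocol's imaging-or-clinical wording with the SAP's imaging-and-clinical wording.
4. Define the per-protocol set as ITT without major violations for OS and PFS in the protocol synopsis, Protocol 9.2.2.2 and SAP 5.3.
5. State which scan is the first MRI.
6. Either carry the 4-month PFS test into SAP 7.7.2 or list its omission in SAP section 9.

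These are wording changes that need no new data and should be made before database lock. The cost is a PFS estimate that may be slightly less favourable.
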